13.3 ANALYSIS PLAN

13.3.1 ANALYSIS SAMPLES

Screened sample: All participants who undergo screening procedures for purposes of eligibility.

Randomized sample: All participants who undergo random assignment. Participants will be analyzed according to the treatment arm to which they were randomized, regardless of the treatment they actually received.

Safety sample: All participants who undergo random assignment and who receive at least one dose of a study drug. Participants in the safety sample will be analyzed with the arm associated with the medication they actually received, regardless of their random assignment.

Modified intent-to-treat (mITT) sample: All participants who undergo random assignment, who receive at least one dose of both study medications, and complete the baseline NAC assessment (See Appendix 1 and 2). Participants will be analyzed according to the treatment arm to which they were randomized, regardless of the treatment they actually received.

Per protocol (PP) sample: All participants in the mITT sample for whom the primary endpoint is assessed and who are compliant with study treatment, defined as taking at least 50% of SLIT or SLIT placebo tablets and at least 75% of dupilumab or dupilumab placebo injections throughout the treatment period.

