8.5 VISIT WINDOWS

All scheduled study visits will aim to occur within the time limits specified below and may be adjusted based on pollen count and participant availability.

Table 7. Visit Windows all Participants (See Appendices 1-5)

Visit	Visit description	Visit Window
Visit -4	Screening	October 2020 to January 2022
Visit -3	Rescue medication dispensing visit	April 1 to July 31
Visit -2	Baseline In-season assessments	June 1 to July 31
Visit -1	Baseline NAC	September to January
Visit 0	Randomization – 1 st dupilumab/dupilumab placebo dose	≥ 28 days after Visit -1 and before end of February
Visit 1	1 st SLIT/SLIT placebo dose	≥12 hours from Visit 0 and ≥ 7 days prior to Visit 2.
Visits 2-53	Treatment visits	Every 2 weeks from Visit 0 through week 104 +/- 10 days (with at least 7 days between treatment visits)
Visits 54-65	Observation visits	Every 4 weeks from 108 to 156 +/- 14 days
S1	Out of season visit assessment year 1	January to April
S2, S7, S12	Pre-season visit	April to May
S3, S8, S13	In-season visits	May to August
S4, S9, S14	Out-of-season NAC visits	September to January 1, 2 and 3 calendar years after Visit -1 +/- 14 days
S5, S10, S15	Mechanistic draws post NAC visits	≥ 4 weeks post NAC visit (S4, S9, S14) and before end of February each year
S6, S11	Out of Season visit	January to April

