11.3 PARTICIPANT REPLACEMENT

Randomized participants who do not receive study drug will be replaced. Participant recruitment will continue until at least 108 participants are randomized and receive at least one dose of both study drugs.

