Grazax [®] /Grazax [®] Placebo ³		X	X	X	X	X	X	X	X	X	X	X	X	X	X	X	X	X	X	X	X	X	X	X	X	X	X	X
Rhinitis Assessments																												
MRSUI	X																											
Local Laboratory Assessments																												
Urine pregnancy test ⁴	X			X		X		X		X		X		X		X		X		X		X		X		X		X

¹ Randomization dose (visit 0) will be 600 mg, all other doses 300 mg.

² Dupixent[®]/Dupixent[®] placebo may be administered in-clinic or self-administered as detailed in section 3.2.

³ Grazax[®]/Grazax[®] placebo taken once daily.

⁴To be carried out within 4 weeks prior to any injection. If a visit was missed, this may be completed at an even-numbered visit as needed or performed at home.

Clinical Assessments																											
Skin prick test endpoint titration – Phleum pratense	X ⁵																										
Mechanistic Assessments																											
PBMCs	X ⁶																										
Serum FAB antibody assay	X ⁶																										
Serum archive	X ⁶																										
Whole blood flow cytometry (BAT)	X ⁶																										
DNA methylation	X ⁶																										
Nasal brushings	X ⁶																										
Nasal fluid cytokines	X ⁶																										
Whole blood -RNA	X ⁶																										

⁵Clinical assessments are collected 1-3 hours, according to clinical judgement, prior to Dupixent®/Dupixent® placebo administration.

⁶Mechanistic assessments are collected 1-3 hours, according to clinical judgement, prior to Dupixent®/Dupixent® placebo administration.

⁷Prior to home administration of Dupixent or Dupixent placebo, participants will be asked whether there have been any AEs or changes in Concomitant medications. If they report Yes, the study team will assess the changes before they proceed with the injection.

APPENDIX 3. SCHEDULE OF EVENTS TREATMENT YEAR 2

	Dosing Year 2																											
Week	54	56	58	60	62	64	66	68	70	72	74	76	78	80	82	84	86	88	90	92	94	96	98	100	102	104		
Visit	28	29	30	31	32	33	34	35	36	37	38	39	40	41	42	43	44	45	46	47	48	49	50	51	52	53		
General Assessments																												
Adverse events	X	X	X	X	X	X	X	X	X	X	X	X	X	X	X	X	X	X	X	X	X	X	X	X	X	X		
Concomitant medications	X	X	X	X	X	X	X	X	X	X	X	X	X	X	X	X	X	X	X	X	X	X	X	X	X	X		
Study Medications																												
Dupixent®/Dupixent® placebo ¹	X	X	X	X	X	X	X	X	X	X	X	X	X	X	X	X	X	X	X	X	X	X	X	X	X	X		
Grazax®/Grazax® Placebo ²	X	X	X	X	X	X	X	X	X	X	X	X	X	X	X	X	X	X	X	X	X	X	X	X	X	X		

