4. ANALYSIS SAMPLES

- Screened sample: All participants who undergo screening procedures for purposes of eligibility.
- Randomized sample: All participants who undergo random treatment assignment.
- Safety sample: All participants who undergo random treatment assignment and who receive at least one dose of a study drug.
- Modified intent-to-treat (mITT) sample: All participants who undergo random assignment, who receive at least one dose of both study treatments, and complete the baseline NAC assessment.
- Per protocol (PP) sample: All participants in the mITT sample for whom the primary endpoint is assessed and who are compliant with study treatment, defined as taking at least 50% of SLIT or SLIT placebo tablets and at least 75% of dupilumab or dupilumab placebo injections throughout the treatment period. See [Section 7.3](#) for the formula to calculate treatment compliance for each study treatment; for SLIT or SLIT placebo, the primary method of calculating observed doses taken will be used for PP sample determination.

If a participant is administered the incorrect treatment, analyses based on the randomized, mITT, and PP samples will be based on the treatment arm to which they were randomized. Whereas analyses based on the safety sample will be based on the treatment arm associated with the medication they actually received, regardless of their random assignment.

For purposes of grouping participants into the treatment arm they actually received, the following rules apply:

- Participants randomized to double-placebo arm that received at least one dose of SLIT and at least one dose of dupilumab will be considered in the combination of SLIT and dupilumab arm.
 - Also, in the rare eventuality that a participant randomized to double-placebo arm receives zero doses of SLIT and at least one dose of dupilumab, then the actual treatment will be the combination of SLIT and dupilumab arm.
- Participants randomized to double-placebo arm that received at least one dose of SLIT and zero doses of dupilumab will be considered in the SLIT plus dupilumab placebo arm.
- Participants randomized to SLIT plus dupilumab placebo arm that received at least one dose of dupilumab will be considered in the combination of SLIT and dupilumab arm.

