5. ESTIMAND FOR PRIMARY ENDPOINT

The primary estimand is as follows:

- **Population**: The primary analysis population will be defined as all participants defined by the study inclusion/exclusion criteria who fall into the mITT analysis sample: All randomized participants who received at least one dose of both study treatments and completed the baseline NAC Total Nasal Symptom Score (TNSS) assessment.
- **Variable**: The primary endpoint will be the NAC TNSS area under the curve from 0 to 1 hours (AUC_{0-1hr}) at year 3.
- **Intercurrent Events**: No special handling will be employed for intercurrent events including missing data for any reason; data will be analyzed as observed using a treatment policy strategy. Any missing data prior to and including year 3 visit after treatment will be implicitly handled as Missing at Random (MAR) via the primary mixed-effect model described in [Section 9.1.2](#), without explicit imputation.
- **Population-Level Summary**: The population-level summary will be the difference in least square means at year 3 visit between the combination of SLIT and dupilumab arm and the double-placebo arm (analyzed as randomized) from the primary mixed-effect model.

Sensitivity analyses for the primary estimand will modify the handling of intercurrent events as described in [Section 9.1.3](#) below.

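### The mITT set requires a first tablet that is scheduled after the first injection, so the primary analysis can drop randomised, already exposed participants, possibly unequally by arm

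*Protocol*

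**What the plan says.** Three parts of the plan meet here.

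- **Analysis set.** Protocol 13.3.1 admits to the mITT those "who receive at least one dose of both study medications, and complete the baseline NAC assessment". SAP 4 has the same condition, "who receive at least one dose of both study treatments, and complete the baseline NAC assessment". SAP 5 makes this the population of the primary estimand: "All randomized participants who received at least one dose of both study treatments and completed the baseline NAC Total Nasal Symptom Score (TNSS) assessment".
- **Order of first doses.** In the visit-window table of protocol 8.5, randomisation and the first injection are at Visit 0. The first tablet is at Visit 1, to be held "≥12 hours from Visit 0 and ≥ 7 days prior to Visit 2". A footnote to the year-1 schedule (Appendix 2) says of the injection: "Randomization dose (visit 0) will be 600 mg, all other doses 300 mg".
- **Stopping and replacement.** SAP 5 says of intercurrent events that "data will be analyzed as observed using a treatment policy strategy". Protocol 6.5 and 11.4 ask people who stop treatment to keep attending assessments. Protocol 11.3 sets the accrual target: "Participant recruitment will continue until at least 108 participants are randomized and receive at least one dose of both study drugs".

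Two other definitions are looser. The Safety sample (protocol 13.3.1, SAP 4) needs one dose of any study drug. The sample-size text (protocol 13.6) counts 108 randomised participants with a baseline challenge and at least one dose of study drug, and does not ask for both.

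**The concern.** A rule of at least one dose is usually defended on the ground that anyone removed had not yet been exposed, so removal cannot depend on what the drug did. Here the defence covers only people who never receive the injection. Someone who has the injection and stops before the first tablet has been randomised and exposed. In that gap the combination arm has had active dupilumab, while the other two arms have had only a placebo injection.

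Membership of the primary set therefore depends on an event after randomisation that the assigned injection can influence, in one of the two arms of the primary contrast. At stake are the comparability of those arms, the year-3 challenge data of anyone who stops in the gap but stays in follow-up, and the agreement between the analysis set and the treatment policy strategy that the SAP claims.

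**Working it through.** **1. The plan's own figures.** Inputs from protocol 13.6: placebo mean 3.81; SD 1.53, 1.64 or 1.73; 30 evaluable per arm; two-sided 0.05; 80% power. Detectable difference = SD × √(2/30) × (1.960 + 0.842).

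- SD 1.53: 1.107, or 29.0% of 3.81
- SD 1.64: 1.186, or 31.1%
- SD 1.73: 1.251, or 32.8%

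With a three-arm ANOVA error term (87 df) these become 29.4%, 31.5% and 33.2%. The stated 29% to 33% is reproduced. For dropout, 30 / (1 − 0.166) rounds up to 36 per arm, 108 in all, as stated. The sample size is not in question; these figures give the scale.

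**2. Length of the gap.** The minimum is 12 hours. Visit 2 is due at day 14 with a window of 10 days, and Visit 1 must fall at least 7 days before it, so the maximum is 14 + 10 − 7 = 17 days. The 24-day limit between injections in protocol 6.1.2.3 gives the same bound (24 − 7). Appendix 2 lists both visits under Week 0, so 17 days is an extreme.

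**3. A participant who stops in the gap.**

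| Definition | Included? |
|---|---|
| Randomized sample | Yes |
| Safety sample | Yes |
| Sample-size count, protocol 13.6 | Yes |
| mITT and primary estimand population | No |
| Per protocol sample | No |

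No planned analysis of the primary endpoint restores this person. Both multiple-imputation analyses (SAP 9.1.3) work on the same estimand population, and the supportive analysis (SAP 9.1.4) uses the narrower per protocol sample. The baseline challenge condition does no harm, because Visit −1 precedes randomisation.

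**4. Size if the excluded had no benefit.** The documents do not give the number, k, who stop in the gap, so k is assumed. Because accrual continues until 108 have had both drugs, take 36 kept plus k excluded in the combination arm and none excluded in double-placebo. If the kept have effect Δ and the excluded zero, the effect in all exposed is Δ × 36/(36 + k). The mITT effect exceeds it by the proportion k/36.

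- k = 1: 2.8%
- k = 2: 5.6%
- k = 3: 8.3%

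In units, with Δ = 1.186, the shift is Δ × k/(36 + k) = 0.03, 0.06 or 0.09. The standard error of the contrast at 30 per arm and SD 1.64 is 1.64 × √(2/30) = 0.42.

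**5. Size if the excluded would have scored worse and there is no true effect.** Let the excluded be c SD worse at year 3, with c assumed to be 0.5 to 1.5. Bias = k/(36 + k) × c × 1.64.

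| k | Bias (units) | Two-sided rejection rate, 30 per arm |
|---|---|---|
| 0 | 0 | 0.050 |
| 1 | 0.02–0.07 | 0.050–0.053 |
| 2 | 0.04–0.13 | 0.051–0.060 |
| 3 | 0.06–0.19 | 0.053–0.072 |

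**The case against.** Several points on the other side have force.

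- **The numbers may be trivial.** The gap is short, nothing in the documents gives a stopping rate after one injection, and k may be zero. This stands, and it limits the weight of the point.
- **Some added participants would change nothing.** The primary model uses year 1, 2 and 3 challenges. Someone with none of these contributes nothing to it, so only gap-stoppers who attend a later challenge would move the mixed-model estimate. This also stands; step 4 is a worst case.
- **The population is a separate attribute of the estimand.** The SAP states it openly and applies treatment policy within it. That makes the choice transparent. It remains true that stopping before the first tablet happens after randomisation and is handled by removal, while every later stop is handled by keeping the person.
- **Disposition tables will show it.** SAP 6.1 reports the size of each sample by randomised arm and the reasons for stopping each treatment. An imbalance would be visible, but the estimate would be uncorrected.

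A reader might infer more than the documents support. Selection through knowledge of assignment is not supported: participants and site teams are blinded (protocol 3.5.1), so the only arm-related route is an effect of the injection itself. The 2.24-fold risk of injection site reactions (protocol 1.2.2, Table 2) does not show differential stopping. It comes from atopic dermatitis trials of 4 to 52 weeks and is not a rate of withdrawal after a first dose. Taking the excluded out of a fixed 36, as 36/(36 − k) − 1, gives 2.9%, 5.9% and 9.1%, but that ignores the continued accrual in protocol 11.3.

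**Conclusion.** The point holds as a defect in the definition of the analysis set. The mITT can remove randomised, exposed participants after an injection that is active in only one arm. This is inconsistent with the treatment policy strategy of SAP 5 and differs from the sample-size text.

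The documents do not show that anyone was lost in this way or that the primary result is biased. With no losses there is no bias. With 1 to 3 losses, all in the combination arm and all without benefit, the overstatement is about 2.8% to 8.3% of the effect, well below one standard error. Those figures rest on assumed counts and outcomes, and on the excluded staying to be measured. The case for change is that the exclusion is avoidable and could favour the tested arm; a large effect is not expected.

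**What to change.** In protocol 13.3.1 and SAP 4 and 5, define the mITT as all randomised participants with a completed baseline challenge and at least one dose of either study drug, analysed as randomised. Keep the set with both drugs as a supportive analysis. The only treatment-related exclusion left is then of people who received neither drug, and the definition agrees with protocol 13.6.

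A note appended to the SAP was written after database lock. If the primary set can no longer change, leave it and add the broader set as a clearly labelled sensitivity analysis. In that case also report, by arm and reason, how many were lost between Visits 0 and 1.

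The cost is small and no new data are needed. The estimand population and the per protocol definition both refer to the mITT and need matching edits. Per protocol membership would not change, since it already requires at least half of the tablets. A few added participants may lack any later challenge; the mixed model would not use them, and the planned multiple imputation can cover them.

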13.3.2 PRIMARY ANALYSIS OF PRIMARY ENDPOINT

The primary analysis will compare the mean TNSS AUC_{0-1hr} between treatment arms using a longitudinal repeated measures model on data from the modified ITT sample at years 1, 2, and 3. The model will include fixed effects for treatment arm, time, and treatment arm by time interaction and will include covariates for baseline TNSS AUC_{0-1hr}. Since a nonlinear relationship between TNSS AUC_{0-1hr} and time is expected, time will be treated as a categorical variable. An unstructured covariance structure will be used to model the correlation among time points within a participant. The primary objective will be addressed by applying a contrast in least squares means at year 3 between the combination of SLIT and dupilumab arm and double-placebo arm. The p-value associated with this contrast will not be adjusted for multiplicity.

13.3.3 SUPPORTIVE ANALYSES OF THE PRIMARY ENDPOINT

Supportive analyses of the primary endpoint will include replication of the primary analysis of the primary endpoint using participants included in the PP sample.

Subgroup analyses of the primary endpoint will include repeating the primary analysis of the primary endpoint using a longitudinal repeated measures model adjusting for treatment arm, time, baseline TNSS AUC_{0-1hr}, and the ratio of grass sIgE to total IgE (or grass skin prick test). An interaction term will also be included between the ratio of grass sIgE to total IgE and treatment arm (or grass skin prick test and treatment arm) to evaluate if the treatment effect on the primary endpoint is modified by differing levels of the ratio of grass sIgE to total IgE (or grass skin prick test).

There will be no methods of imputation used for missing data for the summaries, the primary analysis of the primary endpoint, or supportive analyses of the primary endpoint listed above. Sensitivity analyses of the primary endpoint will address the impact of missing data. First, we will compare demographic characteristics and baseline assessments among subgroups defined by study completion status to identify possible differences of interest. Then, while it is not expected, intermittent missing data will first be imputed using the Markov Chain Monte Carlo (MCMC) method which is appropriate for non-monotonic missing data. Monotone missing data (i.e., data missing after participants discontinue the trial early) will then be multiply imputed using a regression method adjusting for treatment arm, baseline TNSS AUC_{0-1hr} and other covariates as appropriate. There will be 100 samples imputed for analysis. Results of the statistical analysis method on the 100 multiply imputed data sets will be summarized. The overall estimate will then be compared to the estimate derived from the primary inferential analysis model to assess the potential magnitude and direction of bias.

13.3.4 ANALYSES OF SECONDARY ENDPOINTS

All secondary endpoints will be treated as supportive. P-values computed for analyses of secondary endpoints will not be adjusted for multiplicity. Unless otherwise noted, all analyses will be performed on data from the modified ITT sample using a similar model methodology as described in Section 13.3.2.

13.3.4.1 Clinical Tolerance Endpoints

Peak nasal inspiratory flow, defined as the change in PNIF relative to the pre-allergen exposure PNIF measurement during the NAC (Delta PNIF AUC_{0-1hr}), will be analyzed using a longitudinal repeated measures model on data from years 1, 2, and 3 with a covariate for baseline Delta PNIF AUC_{0-1hr}.

The size of the early intradermal test response will be analyzed using a longitudinal repeated measures model on data from years 1, 2, and 3 with a covariate for the size of the early intradermal test response at baseline. A similar model will be used to analyze the late intradermal test response.

The size of the skin prick test endpoint titration response will be analyzed using a longitudinal repeated measures model on data from years 1, 2, and 3 with a covariate for the size of the skin prick test endpoint titration response at Visit 0.

Weekly seasonal symptoms (VAS 0-10 cm), CSMS and miniRQLQ will be summarized separately using the trapezoidal rule to estimate the VAS AUC, CSMS AUC, and miniRQLQ AUC at baseline, year 1, 2, and 3 respectively. The AUC of pollen counts collected weekly during the pollen season in year 1, 2, and 3 will be estimated similarly. A longitudinal repeated measures model will be applied to VAS AUC, CSMS AUC, and miniRQLQ AUC from years 1, 2, and 3 with a time-varying covariate for the AUC of pollen count and a covariate for baseline VAS AUC, baseline CSMS AUC, or baseline miniRQLQ AUC respectively.

MRSUI will be analyzed using a longitudinal repeated measures model on data measured twice (in-season in June/July and out-of-season in November/December) in years 1, 2, and 3 with a time-varying covariate for baseline in-season and out-of-season MRSUI.

Global Evaluation No. 1 will be analyzed using a longitudinal repeated measures model on data from years 1, 2, and 3 with a covariate for baseline Global Evaluation No. 1.

Global Evaluation No. 2 will be analyzed using a longitudinal repeated measures model on data from years 1, 2, and 3 without any additional covariates.

Using each of the above models, Secondary Objective 1 will be addressed by applying a contrast in least squares means at year 3 between the combination of SLIT and dupilumab arm and double-placebo arm.

13.3.4.2 Clinical Desensitization Endpoints

Using the models specified in Section 13.3.2 and in Section 13.3.4.1, Secondary Objective 2 will be addressed by applying a separate contrast in least squares means at year 1 and 2 between the combination of SLIT and dupilumab arm and double-placebo arm.

13.3.4.3 Safety Endpoints

AEs will be summarized during screening, at baseline, and during year 1, 2, and 3 separately. Frequency of AEs will be tabulated by SOC and preferred term, as well as by seriousness, severity, and treatment relatedness. Frequency of SAEs will be tabulated by SOC and preferred term, as well as by severity and treatment relatedness. Frequency of AEs and SAEs by severity will be tabulated across all severity scales, as well as within each severity scale separately. The proportion of participants experiencing at least one AE related to the study therapy regimen during year 1, 2, and 3 will also be reported. AE summaries during screening will be performed using the Screening Sample. All other AE summaries will be performed separately in each treatment arm using the Safety Sample.

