3.3 SECONDARY ENDPOINTS

Clinical tolerance endpoints at year 3, one year after completion of study treatment. The comparison will be between the combination of SLIT and dupilumab and the double-placebo arms.

1. Peak nasal inspiratory flow (Delta PNIF AUC_{0-1hr})
2. Size of early and late intradermal skin test response
3. Size of the skin prick test endpoint titration response
4. Seasonal outcomes
 - a. Weekly seasonal symptoms (Visual Analogue Scale [VAS] 0-10 cms) and combined symptom medication scores (CSMS)
 - b. Weekly rhinitis quality of life scores (Juniper mini-Rhinoconjunctivitis Quality of Life Questionnaire [miniRQLQ]) measured in-season
 - c. Modified Rhinitis Symptom Utility Index (MRSUI) measured in-season and out-of-season
 - d. Global Evaluations No. 1 and No. 2 after the season

Clinical desensitization endpoints at year 1 and 2 whilst on study treatment. The comparison will be between the combination of SLIT and dupilumab and the double-placebo arms.

5. TNSS AUC_{0-1hr}
6. Delta PNIF AUC_{0-1hr}
7. Size of early and late intradermal skin test response
8. Size of skin prick test endpoint titration response
9. Seasonal outcomes
 - a. Weekly seasonal symptoms (VAS 0-10 cms) and CSMS
 - b. Weekly rhinitis quality of life scores miniRQLQ measured in-season
 - c. MRSUI measured in-season and out-of-season
 - d. Global Evaluations No. 1 and No. 2 after the season

Safety Endpoints

10. The number, severity, and relatedness of local and systemic AEs and SAEs reported during screening, at baseline, during years 1 and 2 whilst on study treatment, and during year 3 (one year after completion of study treatment). Each treatment arm will be summarized separately.

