6.5 PREMATURE DISCONTINUATION OF INVESTIGATIONAL AGENT

Study therapy may be prematurely discontinued for any participant for any of the reasons listed in Section 11.2.

Study therapy may also be prematurely discontinued for any participant if the investigator believes that the study treatment is no longer in the best interest of the participant.

Participants who discontinue or are discontinued from the use of study treatment will be invited to continue participating in the study and undergo evaluations per protocol for the remaining duration of the study.

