10.3. Adverse Events

Adverse events for this study are defined as per the protocol section 12.2.1.

For purposes of analysis, treatment-emergent adverse events (TEAEs) will be defined as all reported AEs with a start date on or after the first date of study treatment.

In order to assign treatment-emergence status, partial or completely missing AE start dates will be imputed using the algorithm in [Appendix 15.3](#).

All AEs will be classified by system organ class (SOC) and preferred term (PT), according to Medical Dictionary for Regulatory Activities (MedDRA), version 23.1 or later.

The severity of AEs will be classified using various grading criteria depending on the type of AE as follows:

Type of AE	Name of Severity Grade Criteria	Grading Scale
All local reactions to SLIT	Grading Table for Local Reactions to SLIT	Grade 1, 2, 3, or 4
All local reactions to allergen skin testing	Grading Table for Local Reactions to Allergen Skin Testing	Grade 1, 2, or 3
All local reactions to the NAC procedure	NAC procedure (local reactions)	Grade 1, 2, 3, or 4
Any immediate (0-1hr) systemic allergic reaction that occurred following administration of either SLIT or dupilumab All systemic reactions related to allergen skin testing or to the NAC procedure	WAO Subcutaneous Immunotherapy Systemic Reaction Grading System	Grade 1, 2, 3, 4, or 5 (where 5 = death)

DAIT NIAID Immune Tolerance Network
Statistical Analysis Plan - ITN084AD GRADUATE

All local reactions to dupilumab All other AEs	National Cancer Institute's (NCI's) Common Toxicity Criteria for Adverse Events (CTCAE) v5.0	Grade 1, 2, 3, 4, or 5 (where 5 = death)
---	--	---

Note: See protocol section 12.3.1 for the definitions of each grading criteria.

Each AE is entered on the case report form (CRF) once at the highest severity. As such, no additional data manipulation is needed to identify events.

AE summaries during screening (i.e., any time pre-treatment for treated participants, or during screening period for non-treated participants) will be performed using the Screened sample. All other AE summaries will be performed for only treatment-emergent events by treatment arm using the Safety sample.

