Summary tables will present the total number of events, as well as the number and percentage of participants experiencing the events. If a participant experiences the same AE on multiple occasions, the event will be counted for each occurrence when reporting the number of events. When reporting the number of participants experiencing the events, a participant will only be counted once if they experience an event within the particular SOC or PT. Percentages will be based on the number of participants in the analysis sample of interest.

In addition to the above treatment-emergent summaries at any time post-treatment, AEs will be summarized during year 1, 2, and 3 separately using the following displays:

- Overall summary (repeated with same categories as above)
- Any AE by SOC/PT
- AEs by maximum severity (all severity grade criteria combined)
- SAEs by maximum severity (all severity grade criteria combined)
- AEs by relationship to study drug

For the above AE year intervals, the analysis windows are as follows for counting events:

Year Interval	Lower Bound	Upper Bound
Year 1 (Week 0 through <Week 54)	Study Day 1 (first treatment date)*	Study Day 377
Year 2 (Week 54 through < Week 108)	Study Day 378	Study Day 755
Year 3 (Week 108 onwards)	Study Day 756	No upper bound

*Study day is defined per [Section 8](#) of this SAP.

The denominators for percentages will be for each time interval as follows:

Year Interval	Denominator Subset
Year 1 (Week 0 through <Week 54)	All participants in the Safety sample
Year 2 (Week 54 through < Week 108)	All participants in the Safety sample who remained in the study through Study Day 378
Year 3 (Week 108 onwards)	All participants in the Safety sample who remained in the study through Study Day 756

The study day for inclusion for denominators will be based on the maximum of 1.) end of study date, 2.) date of most-recent follow-up, and 3.) last AE start date.

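### The any-time treatment-emergent AE tables pool dosing with drug-free time, and the yearly tables, cut by study day, give no participant-level incidence over the dosing period

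*Protocol*

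**What the plan says.** The protocol's safety endpoint (3.3, item 10) distinguishes years 1 and 2, on study treatment, from year 3, after it. For the analysis, Protocol 13.3.4.3 states that "AEs will be summarized during screening, at baseline, and during year 1, 2, and 3 separately".

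SAP 10.3 states that "treatment-emergent adverse events (TEAEs) will be defined as all reported AEs with a start date on or after the first date of study treatment". It gives no upper limit. Apart from the screening tables, "All other AE summaries will be performed for only treatment-emergent events by treatment arm using the Safety sample". The overall summary and the SOC/PT tables (any AE, severity, relatedness to drug and to procedure) use this set.

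The same section then adds yearly output, which it introduces with the words "In addition to the above treatment-emergent summaries at any time post-treatment". The yearly displays are the overall summary with the same categories, any AE by SOC/PT, AEs and SAEs by maximum severity with the scales combined, and AEs by relationship to study drug. The windows are Study Days 1–377, 378–755, and 756 onwards. The Year 2 and Year 3 denominators are restricted to participants still in the study at Day 378 and Day 756.

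Two other provisions matter. Participants who stop study treatment "will be invited to continue participating in the study and undergo evaluations per protocol for the remaining duration of the study" (Protocol 6.5). SAP 10.2 plans no exposure summary beyond treatment compliance.

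**The concern.** Protocol 5.2.3 says that there are no human data on giving these two products together, so the by-arm AE picture during exposure is a central safety result. A treatment-emergent set with no end adds drug-free time to every arm. If an excess of events occurs only during dosing and the background events carry on afterwards, the added time raises the percentages in both arms and brings their ratio closer to 1. The combination would then look somewhat better against double-placebo than it did while participants were taking it.

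The yearly tables could answer this, but they do so only in part. Their limits are fixed study days, so they do not follow a participant who stops dosing early. Early stopping may also be linked to harm, because Protocol 11.2 makes a related AE of grade 3 or higher an individual stopping rule.

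**Working it through.** **1. The SAP windows.** 54 × 7 = 378 and 108 × 7 = 756, which match the stated Day 378 and Day 756 limits.

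**2. Drug-free share of the any-time tables.** Protocol 3.1 gives 104 weeks of treatment and 52 weeks of observation: 52/156 = 33% for a completer. The visit windows in Protocol 8.5 can move this for an individual. With 29 drug-free weeks (assuming Visit -1 at the start of September, Visit 0 at the end of February, the year 3 NAC at the early edge of its 14-day tolerance and S15 four weeks later) it is 29/133 = 22%. With 74 (assuming Visit 0 in late September 2021 and S15 at the end of February 2025) it is 74/178 = 42%.

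**3. Drug-free time inside the yearly tables.**
- Completer: week 104 is Day 104 × 7 + 1 = 729. Year 3 starts on Day 756, so Days 730–755 (26 of the 378 days in Year 2, 7%) are off drug but count in Year 2.
- Hypothetical participant who stops both products at week 26 and stays in follow-up: 54 − 26 = 28 weeks of Year 1 and all 54 weeks of Year 2 are off drug, or 82/108 = 76% of the Year 1–2 time. In the any-time tables the share is (156 − 26)/156 = 83%.

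**4. Can the yearly tables be combined?** Event counts can be added across Years 1 and 2. Participant counts cannot, because one person can have an event in both years and the denominators differ.

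**5. What is not repeated by year.** The SOC/PT tables of AEs and SAEs by severity within each scale, and of AEs by relationship to study procedure, exist only in any-time form. The yearly overall summary does carry the scale-specific severity and procedure-relatedness categories, but without SOC/PT.

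**6. Size of the dilution, common events.** Assumptions, none from the documents: constant placebo rate λ per year, rate 2λ on drug for 2 years, and λ in both arms for 1 year afterwards. The risk of at least one event is 1 − exp(−cumulative rate). On-treatment risks are 1 − exp(−4λ) and 1 − exp(−2λ). Any-time risks are 1 − exp(−5λ) and 1 − exp(−3λ).

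| λ | On-treatment, drug v placebo | RR | RD (points) | Any-time, drug v placebo | RR | RD (points) |
|---|---|---|---|---|---|---|
| 0.1 | 33.0% v 18.1% | 1.82 | 14.8 | 39.3% v 25.9% | 1.52 | 13.4 |
| 0.3 | 69.9% v 45.1% | 1.55 | 24.8 | 77.7% v 59.3% | 1.31 | 18.3 |
| 0.6 | 90.9% v 69.9% | 1.30 | 21.0 | 95.0% v 83.5% | 1.14 | 11.6 |

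Differences are taken before rounding. The event-rate ratio moves from 2.0 to (2 × 104 + 52)/156 = 1.67. The expected difference in event counts is 4λ − 2λ on treatment and 5λ − 3λ at any time, so it is 2λ both ways.

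**7. A rare event.** Protocol Table 2 gives conjunctivitis in 8.0% on dupilumab and 3.6% on placebo in atopic dermatitis. Treat these, as an assumption, as 2-year risks. The background risk for one further year is 1 − √(1 − 0.036) = 1.8%. Any-time risks become 9.7% and 5.4%. The RD moves from 4.4 to 4.3 points and the RR from 2.22 to 1.81.

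**8. Administration-site reactions.** With no tablets or injections in the observation phase, new events should be close to zero in all arms. Adding zero leaves both the ratio and the difference as they were.

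**The case against.** The strongest reply is that the SAP does what the protocol asks. The protocol wants yearly summaries and SAP 10.3 supplies them. Neither the safety endpoint nor 13.3.4.3 asks for a figure pooled over years 1 and 2 or for a cut at last dose. This stands. A reader who sees only the definition of a treatment-emergent event might infer that the SAP drops the protocol's split, but the documents do not support that.

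A reader might also infer that no planned table shows AEs during dosing. That goes too far. For participants who keep dosing, the Year 1 window lies wholly within the dosing period and Year 2 does so except for 26 days. Harm that appears early and subsides, as Protocol 5.1.1 describes for SLIT local reactions, would show more sharply in the Year 1 table than in a two-year on-treatment table.

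A third inference is that pooling dilutes every drug harm. Steps 6 to 8 show otherwise. The model also assumes no treatment effect after dosing, whereas the trial is designed to look for a lasting effect, and an open-ended set would capture delayed harm. Planned follow-up is the same in all arms. The SAP tabulates counts and percentages, with no ratio or test for safety, so no error rate or power is at stake.

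The reply does not cover participants who stop early and stay, the missing participant-level incidence over dosing, or the SOC/PT tables that exist only in pooled form. The documents do not say how many such participants to expect. The 16.6% in Protocol 13.6 concerns missing year 3 NACs, which is a different quantity.

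**Conclusion.** The point holds as a limited gap in safety reporting. The any-time tables carry about one-third drug-free time for a completer, and no planned table gives, by arm, the proportion of participants with an event while exposed. For common AEs with an excess confined to dosing and a continuing background, the loss is appreciable: under an on-drug rate ratio of 2, the participant-level RR falls from 1.82 to 1.52, from 1.55 to 1.31 and from 1.30 to 1.14 at assumed placebo rates of 0.1, 0.3 and 0.6 per year. For rare events the risk difference hardly moves, and administration-site reactions are little affected. The yearly tables keep an on-treatment signal largely visible. How far they blur depends on the number and timing of early treatment stoppers who stay in follow-up, which the documents do not give.

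**What to change.** In SAP 10.3:
- Define an on-treatment period from first dose to each participant's last dose of either product (whichever is later) plus one fixed window. The sponsor sets its length without reference to by-arm AE data.
- Add the overall, SOC/PT, severity and drug-relatedness tables by arm for this period, and show the post-treatment period separately.
- Label the existing any-time tables as whole-study, and keep the yearly tables.

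The dates exist: SAP 6.3 already sorts medications by first and last dose and has an after-treatment category, and SAP 6.1 lists treatment discontinuation dates. The note appended to the SAP shows that the database has been locked, so the new tables should be marked as added after lock and recorded with the other changes in SAP 13. The cost is one extra set of tables and the need to choose and justify the window.
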